We will expand eligibility criteria to include women and people with SUD living in marginalized communities who have not been previously incarcerated. While women comprise a smaller percentage of people with SUD, they experience significant barriers to SUD treatment.⁹ Our pilot study showed that women started the CW intervention with worse outcomes when compared to men but had significantly higher reductions of ASM.¹⁰ While the original CW intervention was developed with and for formerly incarcerated people, it addresses concepts that are relevant to all people with SUD living in marginalized communities. Hence, the 3CB has recommended that we expand our eligibility criteria to reach a more diverse group of people. Our 2^3 full factorial design will examine change in attendance (N=128). Data will be collected at baseline and three months post-baseline. This study will impact public health as it will improve the potency of an optimized multi-level intervention adaptable to address different health inequities.

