People interested in the study will call the study's number. A trained master's level clinician will conduct a brief phone screening to obtain self-reported eligibility on SUD, age, contact information, and whether they are currently under supervision. We will have recruitment quotas of 64 people based on self-reported gender (self-identified as men or woman) and supervision status. Intervention groups will be gender specific following recommendations from the literature and our previous CW pilot study. Phone screened participants will be invited to attend an in-person group orientation session to learn about the study, including randomization procedures and the different forms of CW delivery they may receive. Those interested will be invited to complete the baseline survey online in RedCAP. The survey will include a screening informed consent and an eligibility screen with a computerized Global Appraisal of Individual Needs-Substance Problem Scale (GAIN-SPS).³⁵ Those who are eligible and agree to the procedures will be consented and invited to complete the baseline assessment. Follow-ups will be completed online using RedCAP three months post baseline. Baseline and follow-up will include questions about SUD treatment services received over the past 3 months, the Timeline Follow Back questionnaire to measure alcohol, cannabis, cocaine, opioid, and heroin use in the past 30 days, and demographics. Follow ups will also include intervention satisfaction measures and questions about intervention attendance. Surveys will take 30 minutes to complete. Participants will receive \$20 for baseline and \$30 for follow up assessment. Intervention attendance will be recorded weekly in RedCAP by the peer facilitator. After the baseline assessment, participants will be asked to provide extensive locator information, including formal and informal contacts who can reach the participant in a variety of contingencies. Computer generated randomly permuted blocks will be used to assign participants into one of eight experimental conditions. Randomization will occur in Redcap immediately after completing the baseline and be stratified by gender. The research assistant will call participants after randomization to schedule the group's start date. The attached study flowchart summarizes all study procedures.

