To test the objective 'What combination of interventions was associated with higher attendance?', we used a logistic regression model to test the association of group type (open vs closed), incentivizing intervention attendance (incentive vs not) and surveillance (under surveillance vs not) with the outcome of attending 50% of sessions or more (vs not). The logistic regression model included main effects, as well as all 2-way interactions and a 3-way interaction using multiplicative terms. The model was adjusted for job search status, sex, race and ethnicity, marital status income, number of days paid in the past 30 days, and employment status. Parameter estimates (coefficients) and their standard errors were reported. Since the outcome for logistic regression model is the log odds of attending 50% or more sessions, parameter estimates (regression coefficients) represent the change in the odds of the outcome on the log scale for a one-unit change in the independent variable (or at one level compared to its referent if continuous). Thus, parameter estimates were transformed by taking the exponent to facilitate interpretation as odds ratio. Exponentiated coefficients are interpreted as the difference in the likelihood (odds) of achieving the outcome between those who received an intervention component compared to those who did not receive it, collapsing (averaging) over levels of the other components and controlling for covariates. To calculate percent change, exponentiated coefficients are compared to the value of one (one means no difference). A value that is greater than one or less than one, indicates that the outcome is more likely or less likely to occur, respectively. Thus, we subtract one from the exponentiated regression coefficient to obtain the magnitude of change in the outcome, and when multiplied by 100 it is a percent change in the outcome.

To test the objective 'Does higher attendance result in less ASM use?' we employed a generalized multiple regression model testing the association of attendance rates (continuous variable), incentivizing intervention attendance (incentive vs not), surveillance (under surveillance vs not) and their 2-way interaction with the outcome of percent of ASM at follow up, adjusting for demographic characteristics and percent of ASM at baseline. We analyzed the intervention components using effect coding (1 vs -

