1). Thus, the parameter estimates (regression coefficients) that included intervention components were multiplied by a scaling constant of 2 to obtain the main and interaction effects as per guidelines for using effect coding in multiple regression. We did not include group type in this model because group type did not meet our selection criteria for inclusion in the optimized intervention. Due to the skewness of the ASM variable, we assumed a negative binomial distribution, thus we calculated the exponent of these scaled parameter estimates to facilitate interpretation as the percentage of ASM use. For interpretation, exponentiated coefficients are compared to the value of one to estimate a percent change, as was explained for the logistic regression model.

For all models, fit was assessed using standard criteria including the Akaike Information Criterion (AIC), Pearson Chi-Square, and Wald test. Analyses were conducted using SAS version 9.4 (SAS Institute, Cary, NC), using two-sided tests and a significance level of 0.05.

Using the causal mediation approach, we tested the mediation of incentivizing intervention attendance on the relationship between attendance with the outcome of percent of ASM at follow up, adjusting for demographic characteristics and mean percent of ASM use at baseline. Since no mediation effect was noted, no results are shown.

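### The ASM model appears to enter baseline use as one linear term under a log link; without a zero-use term this can bias the attendance effect, by an amount the documents do not settle

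*SAP*

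**What the plan says.** The SAP's second objective asks whether higher attendance leads to less ASM. Its model tests the "association of attendance rates (continuous variable"), incentive, supervision and a two-way interaction against percent ASM at follow-up, "adjusting for demographic characteristics and percent of ASM at baseline".

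On the distribution the SAP states: "Due to the skewness of the ASM variable, we assumed a negative binomial distribution". No link is named, but "exponentiated coefficients are compared to the value of one to estimate a percent change", which implies a log link. Fit is checked as follows: "fit was assessed using standard criteria including the Akaike Information Criterion (AIC), Pearson Chi-Square, and Wald test". None of these checks is aimed at the shape of the baseline term or at people with no baseline use.

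Protocol Section 7F measures ASM with "the Timeline Follow Back questionnaire to measure alcohol, cannabis, cocaine, opioid, and heroin use in the past 30 days". Section 10A requires a substance use disorder and states no recent-use requirement. Half the sample is to be under supervision.

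**The concern.** Under a log link, a linear baseline percent says that each extra 10 points of baseline use multiplies follow-up use by the same factor anywhere between 0% and 100%. If use persists roughly in proportion, the log of the follow-up mean instead climbs steeply near zero and then flattens. The misfit would then be largest among people at exactly 0%.

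This matters because attendance was not randomised. Baseline ASM is the main listed protection against severity confounding the attendance coefficient, and that coefficient is to be read as the effect of attending on ASM. The protocol gives reasons why attendance might track use. Section 13D lists regularly arriving high among the signs that may lead to withdrawal. Section 13A lets Drug Court participants count completion towards a mandate. Supervision is in the model and absorbs part of the second link, but not differences within supervision groups.

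**Working it through.** The documents give no effect size, power or error rate for this model, so there is no stated figure to reproduce.

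**From the documents:** 128 planned (Protocol Section 6), number analysed not given; 8 sessions (Section 7D); a 30-day measure (Section 7F); two-sided 5% tests (SAP).

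**Assumed:** the share with zero baseline use, their attendance gap, and their follow-up use.

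**Step 1: shape.** Take the implied model, demographics omitted, as log E(Y) = β0 + β1·attendance + β2·incentive + β3·supervision + β4·incentive·supervision + γ·baseline. A linear term forces one factor, exp(10γ), per 10 points. Compare two assumed persistence lines:

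- Follow-up = 0.04 + 0.75 × baseline. From 0 to 10%: 0.115/0.04 = 2.88. From 50 to 60%: 0.49/0.415 = 1.18.
- Follow-up = 0.15 + 0.5 × baseline. From 0 to 10%: 0.20/0.15 = 1.33. From 50 to 60%: 0.45/0.40 = 1.13.

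The departure is large under the first line and mild under the second.

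**Step 2: when it becomes bias.** Let δ be the zero-users' true log mean minus the value the fitted curve extrapolates to at 0%. Let Δ be their attendance minus everyone else's. The attendance coefficient is pushed in the direction of δ × Δ. If either is zero, this bias is absent.

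**Step 3: size in large samples.** Negative binomial fits used a log link, the terms in Step 1 and N = 20,000. The true ratio was 1, and users' follow-up mean was 0.7 × baseline. Entries are false ratios for 100% versus 0% attendance.

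| Zero-users' mean follow-up days | Attendance gap | 20% zero-users | 40% zero-users |
|---|---|---|---|
| 0.3 | +0.2 | 0.73 | 0.63 |
| 1 | +0.2 | 0.84 | 0.83 |
| 3 | +0.2 | 1.06 | 1.06 |
| 6 | +0.2 | 1.29 | 1.29 |
| 0.3 | −0.2 | 1.35 | 1.59 |

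With no attendance gap the ratio was 0.95 to 1.06, which is noise. A zero-use indicator returned 0.94 to 1.05. A gap of 0.2 is 0.2 × 8 = 1.6 sessions.

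**Step 4: size at N = 128** (800 replicates, zero-users at 0.3 days).

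| Zero-users | Gap | Median ratio, linear | Rejection, linear | Rejection with indicator |
|---|---|---|---|---|
| 20% | 0 | 1.00 | 11% | 10.5–12.4% |
| 20% | 0.2 | 0.65–0.68 | 17–18% | 9.1–12.0% |
| 20% | 0.3 | 0.56 | 25% | 9.9–12.2% |
| 40% | 0 | 1.05 | 18% | 21.0–22.1% |
| 40% | 0.2 | 0.51 | 31% | 20.7–21.6% |
| 40% | 0.3 | 0.35 | 40% | 22.0–23.3% |

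At a gap of 0.2, the excess over the no-gap rows is 6 to 7 points (20% zero-users) or 31 − 18 = 13 points (40%). At 3 days and a gap of 0.2, linear rejection was 5–6%. At 6 days it was 5%, although the ratio was 1.26–1.27.

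**Step 5: other assumptions**, N = 110, linear term unless stated:

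- Line 0.04 + 0.75 × baseline (zero-users at 0.04 × 30 = 1.2 days), 25% zero-users attending 25 points more. Three runs with differing baseline and attendance distributions or model terms gave 0.73, 0.64 and 0.52, with rejection of 14%, 16% and 19%. The indicator gave 0.97 to 1.00 and 6–8%. Attending 25 points less gave 1.40 and 1.73 in the two runs that tried it.
- Same line, 10-point gap: 0.92 (10% zero-users) and 0.79 (25%), rejection 2.5–4.5%.
- Line 0.15 + 0.5 × baseline (0.15 × 30 = 4.5 days): 0.87 to 0.99, rejection at most 7%.
- Line 0.01 + 0.75 × baseline (0.3 days), 25% zero-users, 25-point gap: 0.40, rejection 33%.
- A fractional logit in place of the negative binomial: odds ratio 0.85 with the linear term, 0.99 with the indicator.

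**Control.** When the truth was exactly log-linear in baseline percent, the linear model gave 0.97 to 1.03 with rejection of 6–8%, even with a 0.2 gap.

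**The case against.** The case on the other side has several parts, and much of it stands.

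- **Linear entry is inferred.** The SAP never states a functional form. This stands, but the request to state the form holds either way.
- **Zero-users may be few.** The measure spans alcohol and several drugs, so if these are combined a zero means none of them for 30 days. The look-back window of the screening instrument is not given. Inpatients appear only as a ticked box in Protocol Section 9B. Zero baseline use is therefore possible, but not shown to be common.
- **Every driving input is assumed.** Small gaps or strong regression to the mean leave little bias. This stands.
- **Supervision is already adjusted for.** It removes part of the pathway. The false ratios in Steps 3 and 4 arose with supervision in the model, so it need not remove all of it.
- **The larger problems lie elsewhere.** Attendance is not randomised, and a negative binomial for a bounded percent rejected 11–18% with no attendance gap at all. This stands; the indicator does not cure either.

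A reader might infer that differing attendance by zero-users is enough to produce a false effect, or that the effect would make attendance look beneficial whenever abstinent people attend more. Neither follows. The bias also needs zero-users' follow-up use to depart from the extrapolated curve; in Step 3 it nearly vanishes at 3 days and reverses at 6.

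**Conclusion.** The concern holds as a conditional weakness in the specification. With the natural reading of the SAP, baseline severity is adjusted for in a form that can fail for people with no baseline use, and the listed fit checks are not designed to show it.

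When zero-users stay near abstinent (0.3 of 30 days) and attend 20 points more or less than others, the false ratio is about 0.6 to 1.6 where the truth is 1. Harsher assumptions go further, such as 0.35 at N = 128 with 40% zero-users and a 30-point gap. When zero-users average about 3 days at follow-up, or attend no differently, it is close to 1.

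The documents report neither the share of zero-users, nor their attendance, nor their follow-up use. Direction and size in this trial therefore cannot be determined, and no single figure above, including 0.73 with 14% false positives, is an estimate for it. The point is still worth acting on: it bears on a named objective, a reader cannot discount for a bias of unknown sign, and the remedy uses data already collected.

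**What to change.** 1. State the functional form used for baseline percent ASM.
2. Keep baseline percent ASM and add an indicator for no use in the 30 days before baseline, or use a restricted cubic spline. Do this in the ASM model and in the mediation model with the same outcome, whatever distribution is used.
3. Report the number of zero-users, their attendance and their ASM at follow-up.
4. Show the attendance effect with and without the added term. Because the SAP already reports a result, label the refit as added after the analysis.

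Possible SAP wording: *Baseline percent ASM enters as a linear term together with an indicator for no use in the 30 days before baseline; results without the indicator are also shown.*

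The indicator costs one degree of freedom, a spline somewhat more, plus a refit of the affected models. No new data are needed. The change does not remove other confounding of attendance, nor any miscalibration from applying a negative binomial to a bounded percent; those need separate treatment.
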